#### **Phase II Extended Component:**

The primary goal of the extended component is to study the potential efficacy of GTB-3550 TriKE in this patient population. Efficacy is measured using rates of complete and partial remission. A Simon's MiniMax two-stage design is used in this phase. Stage 1 will enroll 13 patients, including all patients treated at the MTD defined during the dose finding component. If 3 or more of these 13 patients experience a clinical response by Day 42, the trial moves to Stage 2 and enrolls an additional 17 patients. If at least 10 of the 30 patients have a disease response, GTB-3550 TriKE will be considered for further investigation. There is no staggering of enrollment for this cohort.

Primary Objectives:	
Phase I Dose Finding: To identify the maximum tolerated dose (MTD) of GTB-3550 TriKE defined as the dose level that most closely corresponds to a dose limiting toxicity rate (DLT) of 20%.
 
Phase II Extension: To determine preliminary efficacy as measured by the rates of “best” clinical response by Day 42 day after the start of the 1st infusion. For AML clinical response includes complete remission with or without hematologic or platelet recovery (CR, CRI or CRp) or partial response. For MDS clinical response includes complete remission, marrow CR (with incomplete peripheral blood count normalization), partial response or hematologic improvement (HI). For advanced systemic mastocytosis response is considered a decrease in mast cell burden in bone marrow or serum tryptase level by at least 30%.

Secondary Objectives:	

• To evaluate the safety of GTB-3550 TriKE when administered on this schedule

• To estimate overall survival (OS) at 6 months

Correlative Objectives:	

• To monitor the number, phenotype, activation status and function of NK cells, T cells, T regulatory cells and MDSCs pre- and post-therapy ( [REDACTED] [REDACTED] )

• To evaluate the pharmacokinetics and dynamics of the TriKE reagent

• To monitor for the development of human anti-TriKE antibodies

• To monitor the occurrence of antigen negative escape variants ( [REDACTED] ) in patients without response

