**Extended Phase II Component:**

Patients will receive three consecutive blocks of four 24 hour continuous infusions of GTB-3550 TriKE at the Phase I MTD separated by a 72 hour rest. There is no staggering of enrollment for this component.

**Stage 1:** Enroll a total of 13 patients (including all treated at the MTD in Phase I). If 3 or more of these patients have clinical response by Day 42 the trial will continue to Stage 2. If the Phase I component enrolls more than 13 patients at the MTD, the futility rule for the two-stage design will be adjusted with the given number of patients enrolled at the MTD.

**Stage 2:** Enroll an additional 17 patients. If 10 of 30 patients have a clinical response by Day 42, GTB-3550 TriKE will be considered promising for further investigation.

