## 1 Objectives

### 1.1 Primary Objective

Phase I Dose Finding: To identify the maximum tolerated dose (MTD) of GTB-3550 TriKE defined as the dose level that most closely corresponds to a dose limiting toxicity rate (DLT) of 20%.

Phase II Extension: To determine preliminary efficacy as measured by the rates of “best” clinical response by Day 42 after the start of the 1st infusion.

For AML clinical response includes complete remission with or without hematologic or platelet recovery (CR, CRi or CRp) or partial response. For MDS clinical response includes complete remission, marrow CR (with incomplete peripheral blood count normalization), partial response or hematologic improvement (HI). For advanced systemic mastocytosis response is considered a decrease in mast cell burden in bone marrow or serum tryptase level by at least 30%.

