## 12 Statistical Considerations

### 12.1 Study Design and Endpoints

This is a multisite Phase I/II study of GTB-3550 trispecific killer cell engager (TriKE) for the treatment of high risk MDS and relapsed AML. Once the MTD is identified, the objective will be to confirm safety and obtain preliminary estimates of efficacy as measured by the objective response, the **primary trial endpoint** as assessed between Day 21 and Day 42. For AML clinical response includes complete remission with or without hematologic or platelet recovery (CR, CRi or CRp) or partial response. For MDS clinical response includes complete remission, marrow CR (with incomplete peripheral blood count normalization), partial response or hematologic improvement (HI). For advanced systemic mastocytosis response is considered a decrease in mast cell burden in bone marrow or serum tryptase level by at least 30%.

All patients completing Block #1 will be evaluable for DLTs and toxicities. Patients who discontinue therapy prior to completion of both Block #1 and Block #2 will be replaced. Patients completing Block #1 and Block #2, but come off treatment for disease progression, will still be evaluable for efficacy and will not be replaced. If needed a subgroup of patients receiving all 3 blocks will also be evaluated for response as a secondary population. We expect that the number of patients coming off therapy after only completing block #1 will be minimal.

**Secondary trial endpoints** will include toxicity through Day 29 and overall survival (OS) at 6 months from 1st dose of study drug.

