### **Myelodysplastic Syndromes (MDS):**

Category	Response criteria (responses must last at least 4 wk)
Complete remission	
Bone marrow: <math>\leq</math> 5% myeloblasts with normal maturation of all cell lines*
 
 
• Persistent dysplasia will be noted*†
 
 
Peripheral blood‡
 
 
• Hgb <math>\geq</math> 11 g/dL
 
• Platelets <math>\geq</math> 100 <math>\times</math> 10^9/L
 
• Neutrophils <math>\geq</math> 1.0 <math>\times</math> 10^9/L†
 
• Blasts 0%
 

Partial remission	
All CR criteria if abnormal before treatment except:
 
 
• Bone marrow blasts decreased by <math>\geq</math> 50% over pretreatment but still <math>></math> 5%
 
 
Cellularity and morphology not relevant

Marrow CR	
Bone marrow: <math>\leq</math> 5% myeloblasts and decrease by <math>\geq</math> 50% over pretreatment†
 
Peripheral blood: if HI responses, they will be noted in addition to marrow CR†

Stable disease	
Failure to achieve at least PR, but no evidence of progression for <math>\geq</math> 8 weeks

Cytogenetic response	
Complete
 
 
• Disappearance of the chromosomal abnormality without appearance of new ones
 
 
Partial
 
 
• At least 50% reduction of the chromosomal abnormality
 

Hematologic Improvement	
Erythroid response (pretreatment, < 11 g/dL): Hgb increase by 1.5 g/dL Relevant reduction of units of RBC transfusions by an absolute number of at least 4 RBC transfusions/8 wk compared with the pretreatment transfusion number in the previous 8 wk.
 
Platelet response (pretreatment, < 100 X 10^9/L): Absolute increase of < 30 X 10^9/L for patients starting with 20 X 10^9/L platelets Increase from less than 20 X 10^9/L to greater than 20 X 10^9/L and by at least 100%
 
Neutrophil response (pretreatment, < 1.0 X 10^9/L) At least 100% increase and an absolute increase 0.5109/L

MDS indicates myelodysplastic syndromes; Hgb, hemoglobin; CR, complete remission; HI, hematologic improvement; PR, partial remission; FAB, French-American-British; AML, acute myeloid leukemia; PFS, progression-free survival; DFS, disease-free survival.

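### Transfusion-based hematologic improvement needs 8 weeks but the Phase II primary endpoint closes at Day 42 with no linking rule; the platelet line and the synopsis wording also conflict with the endpoint

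*Combined protocol and SAP*

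**What the plan says.** Section 1.1 sets the Phase II primary objective as the rate of best "clinical response by Day 42 after the start of the" first infusion. Its list of qualifying outcomes for MDS ends with "partial response or hematologic improvement (HI"), so HI alone is enough. Section 12.1 repeats the list and describes the endpoint "as assessed between Day 21 and Day 42". The decision rule is 3 or more responders among the first 13 patients to continue, then 10 of 30. The schema ties the final step to the same date: "If 10 of 30 patients have a clinical response by Day 42", the product is considered promising.

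Appendix III, in the MDS table, defines HI:
- **Transfusions (part of the erythroid response):** a reduction of "at least 4 RBC transfusions/8 wk compared with the pretreatment transfusion number in the previous 8 wk".
- **Platelets, first line:** "Absolute increase of < 30 X 10 9 /L for patients starting with 20 X 10 9 /L platelets".
- **Platelets, second line (patients starting below 20):** a rise to above 20 "and by at least 100" per cent.

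The table's heading also requires responses to last 4 weeks.

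The synopsis (Phase II Extended Component) and Section 4 describe the endpoint differently: "Efficacy is measured using rates of complete and partial remission".

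**The concern.** The transfusion criterion needs 8 weeks of observation, but the endpoint that uses it closes after 6. The plan has no prorating rule, no matched baseline period and no rule for patients who cannot be evaluated. Two people scoring the same chart could therefore reach different answers, and the error can run either way.

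The platelet line, read as printed, accepts small rises and rejects large ones. The synopsis and Section 4 would not count HI at all.

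All three points affect the count that is compared with 3/13 and 10/30, so they bear on the main efficacy conclusion. They concern only how response is scored in MDS patients, except that the synopsis wording also leaves out the mastocytosis criterion.

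**Working it through.** **Plan's own figures.** Section 12.3 gives a null response rate of 20%, an alternative of 40%, 30 patients, 80% power and a significance level of 0.05. Exact two-stage binomial calculation for at least 3/13, then at least 10/30, gives power 0.805 and type I error 0.058. Power reproduces. The small excess over 0.05 is a separate matter and plays no part here.

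**Time available.** Day 42 is 42/7 = 6 weeks and Day 21 is 21/7 = 3 weeks, against the 8 weeks in Appendix III. The shortfall is 2 to 5 weeks.

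**Constant transfusion rate.** Let b be units in the 8 weeks before Day 1 and w the weeks observed since Day 1. With no change in need, a raw count gives an apparent reduction of b × (1 − w/8). This reaches 4 when b ≥ 4/(1 − w/8):
- w = 6: 4/0.25 = 16 units per 8 weeks (16 before, 12 after).
- w = 3: 4/0.625 = 6.4, so 7 units per 8 weeks.
- w = 8: the apparent reduction is always 0.

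**Chance variation.** Assume independent Poisson counts at an unchanged rate, with mean b before and bw/8 after. The documents give neither this model nor a range for b; 4 to 16 units per 8 weeks is assumed. The chance of a spurious reduction of at least 4 units is the sum over i ≥ 4 of P(before = i) × P(after ≤ i − 4). For the prorated rule, the second term becomes P(after ≤ (i − 4) × 6/8).

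| b (units/8 wk) | 8 v 8 weeks | Raw 6 weeks v 8 | Raw 3 weeks v 8 | 6 weeks prorated to 8 |
|---|---|---|---|---|
| 4 | 10.5% | 16.8% | 32.1% | 9.8% |
| 8 | 18.9% | 34.1% | 67.0% | 18.6% |
| 12 | 23.6% | 45.4% | 83.9% | 23.5% |
| 16 | 26.7% | 53.6% | 92.0% | 26.6% |

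A raw 6-week count adds between 16.8 − 10.5 = 6.3 and 53.6 − 26.7 = 26.9 percentage points. Prorating removes the excess. If 8 full weeks are required instead, the chance of qualifying by Day 42 is zero for everyone, including a patient who has become transfusion-free.

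**Platelets as printed.** For a patient starting at 20 × 10⁹/L:

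| Rise (× 10⁹/L) | As printed (below 30) | If 30 is a minimum |
|---|---|---|
| 5 | qualifies | does not |
| 29 | qualifies | does not |
| 30 | does not | qualifies |
| 40 | does not | qualifies |

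The second platelet line covers patients starting below 20 and sets a minimum. The natural complement is a minimum for patients starting above 20.

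**Which outcomes count.** Sections 1.1 and 12.1, and the synopsis's own statement of objectives, include HI and marrow CR for MDS and a 30% fall in mast cell burden or tryptase for mastocytosis. The efficacy sentence in the synopsis and Section 4 names only complete and partial remission. These cannot both define the primary endpoint.

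**The case against.** The strongest reply is that Appendix III states a rate per 8 weeks. On that reading, 12 units in 6 weeks is 16 per 8 weeks, an unchanged patient shows no reduction, and nothing is inflated. That is a sensible reading, and the table shows it works. It is not written down, however, and neither of the other two readings is excluded.

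A reader might infer that unchanged patients will be counted as responders and carry the trial past 3/13 and 10/30 without drug activity. The documents do not support that. No section prescribes a raw 6-week count, and requiring 8 full weeks would under-count instead. Even on a raw count, a steady patient needs 16 units per 8 weeks to qualify at Day 42. The rule is sensitive to the response rate: exact calculation gives a 5.8% chance of success at 20%, 15.4% at 24% and 30.5% at 28%. Moving from the Poisson figures to 24% or 28%, however, requires the share of MDS patients and the share who are transfusion-dependent, and the plan gives neither.

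Two further replies have some force. Response follow-up continues to 6 months (Section 4; Section 8.1, footnote 6), so a reduction that starts early could be confirmed later; but the primary endpoint stops at Day 42 and no rule brings later data in. The hemoglobin, platelet and neutrophil routes to HI also remain open, so losing the transfusion route does not remove HI altogether. The 4-week duration requirement does not help: it governs how long a response lasts, not the lengths of the periods compared.

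The platelet sign could be a fault of text extraction. The same cell runs a neutrophil figure together as 0.5109/L and has no comparator before the starting value of 20. Other inequality signs in the table survived, so a typing error in the source is equally possible. The source page must be checked first.

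The efficacy sentence may be loose summary wording, since the same synopsis lists HI under its objectives. It should still be corrected.

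**Conclusion.** The point stands as a mismatch between criterion and endpoint, with direction unresolved. An 8-week transfusion criterion is used in an endpoint that closes at 6 weeks, and the plan does not say how to apply it. Requiring 8 full weeks loses true responders. A raw 6-week count gives spurious responses in 17% to 54% of unchanged patients, against 11% to 27% for equal 8-week windows. Those percentages rest on an assumed Poisson model and assumed rates of 4 to 16 units per 8 weeks, and apply only to MDS patients. No figure for the effect on the 3/13 and 10/30 rule can be supported from the documents.

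The platelet line as printed contradicts its purpose and its companion line, subject to the source check. The summary statement of efficacy contradicts Sections 1.1 and 12.1.

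**What to change.** **(a) Appendix III, transfusion HI.** Score it by Day 42 on a common rate. Count RBC units from Day 1 through Day 42, with the full period required, and prorate them as units × 56 / days observed. Compare with the 8 weeks before Day 1 and keep the reduction of at least 4 units per 8 weeks. Abstract units from the chart for both periods: Section 6.2 documents prior medication for only 14 days before screening, and Section 8.1 has no transfusion entry.

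The cost is a little chart abstraction and a somewhat noisier rate. Under the Poisson assumption, the variance of the difference rises from 2b to b + (4/3)² × 0.75b = 2.33b, about 8% more in standard deviation.

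Matching 42 days to 42 days with 4 units unchanged is less suitable. It raises the bar to 4 × 56/42 = 5.3 units per 8 weeks. A patient steadily on 4 or 5 units per 8 weeks has only 3 to 3.75 units in 42 days and could not qualify even on becoming transfusion-free.

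**(b) Appendix III, platelet HI.** Check the line against the source page. If it is printed as an upper limit, correct it to a minimum increase of 30 × 10⁹/L for patients starting above 20 × 10⁹/L.

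**(c) Synopsis and Section 4.** Replace the reference to complete and partial remission rates with the clinical response defined in Section 1.1.

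Items (b) and (c) are wording changes only. All three should be settled before any Phase II response is scored.

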## Appendix IV - P450 Drug Interactions

### Flockhart Table™

For complete table: <http://medicine.iupui.edu/clinpharm/ddis/clinical-table>  
accessed July 25, 2018

### P450 Drug Interactions select substrates

#### Abbreviated "Clinically Relevant" Table

SUBSTRATES	
2D6	3A4,5,7
Beta Blockers:	Macrolide antibiotics:
carvedilol	clarithromycin
S-metoprolol	erythromycin (not 3A5)
propafenone	NOT azithromycin
timolol	telithromycin
Antidepressants:	Anti-arrhythmics:
amitriptyline	quinidine→3-OH(not 3A5)
clomipramine	
desipramine	
duloxetine	
fluoxetine	
imipramine	Benzodiazepines:
paroxetine	alprazolam
	diazepam→3OH
	midazolam
	triazolam
Antipsychotics:	Immune Modulators:
haloperidol	cyclosporine
risperidone	tacrolimus (FK506)
thioridazine	sirolimus
Others:	HIV Antivirals:
aripiprazole	indinavir
atomoxetine	ritonavir
codeine	saquinavir
dextromethorphan	nevirapine
doxepine	
flecainide	Prokinetics:
mexiletine	cisapride
ondansetron	
oxycodone	Antihistamines:
risperidone	astemizole
tamoxifen	chlorpheniramine
TAMOXIFEN GUIDE	
tramadol	Calcium Channel Blockers:
venlafaxine	amlodipine
	diltiazem
	felodipine

**SUBSTRATES**

2D6

3A4,5,7

nifedipine  
nisoldipine  
nitrendipine  
verapamil

**HMG CoA Reductase Inhibitors:**

atorvastatin  
lovastatin  
NOT pravastatin  
NOT rosuvastatin  
simvastatin

**PDE-5 Inhibitors:**

sildenafil  
tadalafil  
vardenafil

**Others:**

alfentanyl  
aripiprazole  
boceprevir  
buspirone  
carbamazepine  
gleevec  
haloperidol  
pimozide  
quinine  
tamoxifen  
telaprevir  
trazodone  
vincristine

## INHIBITORS

- A Strong inhibitor is one that causes a > 5-fold increase in the plasma AUC values or more than 80% decrease in clearance.
- A Moderate inhibitor is one that causes a > 2-fold increase in the plasma AUC values or 50-80% decrease in clearance.
- A Weak inhibitor is one that causes a > 1.25-fold but < 2-fold increase in the plasma AUC values or 20-50% decrease in clearance.

2D6

3A4,5,7

- bupropion
- fluoxetine
- paroxetine
- quinidine,

- duloxetine

- amiodarone
- cimetidine

- aripiprazole
- diphenhydramine
- chlorpheniramine
- clomipramine
- doxepin
- haloperidol
- methadone
- ritonavir
- terbinafine

### HIV Antivirals:

- indinavir
- nelfinavir
- ritonavir

- clarithromycin
- itraconazole
- ketoconazole
- nefazodone

- erythromycin
- grapefruit juice
- verapamil2

- suboxone
- diltiazem

- cimetidine

- amiodarone
- NOT azithromycin
- fluvoxamine
- troleandomycin
- voriconazole

## INHIBITORS

- A Strong inhibitor is one that causes a > 5-fold increase in the plasma AUC values or more than 80% decrease in clearance.
- A Moderate inhibitor is one that causes a > 2-fold increase in the plasma AUC values or 50-80% decrease in clearance.
- A Weak inhibitor is one that causes a > 1.25-fold but < 2-fold increase in the plasma AUC values or 20-50% decrease in clearance.

2D6

3A4,5,7

■ bupropion  
■ fluoxetine  
■ paroxetine  
■ quinidine1

■ duloxetine

■ amiodarone  
■ cimetidine

aripiprazole  
diphenhydramine  
chlorpheniramine  
clomipramine  
doxepin  
haloperidol  
methadone  
ritonavir  
terbinafine

### HIV Antivirals:

■ indinavir  
■ nelfinavir  
■ ritonavir

■ clarithromycin  
■ itraconazole  
■ ketoconazole  
■ nefazodone

■ erythromycin  
■ grapefruit juice  
■ verapamil2

■ suboxone  
■ diltiazem  
■ cimetidine

amiodarone  
NOT azithromycin  
fluvoxamine  
troleanomycin  
voriconazole

INDUCERS	
2D6	3A4,5,7
	carbamazepine efavirenz nevirapine phenobarbital phenytoin pioglitazone rifabutin rifampin St. John's Wort troglitazone

Metabolizer Phenotypes:

PM = Poor

IM = Intermediate

EM = Extensive

UM = Ultrarapid

The Flockhart Table™ is © 2016 by The Trustees of Indiana University. All rights reserved.

## Appendix V - Combined List of Drugs That Prolong QT/QTc

### CredibleMeds Filtered QTDrug List

The last revision date: May 20, 2018

See Note below for safe use of this Table

Highlighted Drugs are those frequently used in cancer patient care.

The drug list below contains drugs from the categories: Known Risk of TdP And Avoid in congenital long QT

Generic Name	Brand Names (Partial List)	Drug Class	Therapeutic Use	Risk Category	Route
Aclarubicin (Only on Non US Market)	Aclacin, Aclacinomycine, Aclacinon, Aclaplastin, Jaclacin	Anti-cancer	Cancer	Risk of TdP And Avoid in congenital long QT	injection
Amiodarone	Cordarone, Pacerone, Nexterone	Antiarrhythmic	Arrhythmia	Risk of TdP And Avoid in congenital long QT	oral, injection
Anagrelide	Agrylin, Xagrid	Phosphodiesterase 3 inhibitor	Thrombocythemia	Risk of TdP And Avoid in congenital long QT	oral
Arsenic trioxide	Trisenox	Anti-cancer	Cancer (leukemia)	Risk of TdP And Avoid in congenital long QT	injection
Astemizole (Removed from Market)	Hismanal	Antihistamine	Allergic rhinitis	Risk of TdP And Avoid in congenital long QT	oral
Azithromycin	Zithromax, Zmax	Antibiotic	Bacterial infection	Risk of TdP And Avoid in congenital long QT	oral, injection
Bepridil (Removed from Market)	Vascor	Antiangular	Angina Pectoris (heart pain)	Risk of TdP And Avoid in congenital long QT	oral
Chloroquine	Aralen	Antimalarial	Malaria	Risk of TdP And Avoid in congenital long QT	oral
Chlorpromazine	Thorazine, Largactil, Megaphen	Antipsychotic / Antiemetic	Schizophrenia, nausea, many others	Risk of TdP And Avoid in congenital long QT	oral, injection, suppository
Cilostazol	Pletal	Phosphodiesterase 3 inhibitor	Intermittent claudication	Risk of TdP And Avoid in congenital long QT	oral

Generic Name	Brand Names (Partial List)	Drug Class	Therapeutic Use	Risk Category	Route
Ciprofloxacin	Cipro, Cipro-XR, Neofloxin	Antibiotic	Bacterial infection	Risk of TdP And Avoid in congenital long QT	oral, injection
Cisapride (Removed from Market)	Propulsid	GI stimulant	Increase GI motility	Risk of TdP And Avoid in congenital long QT	oral
Citalopram	Celexa, Cipramil	Antidepressant, SSRI	Depression	Risk of TdP And Avoid in congenital long QT	oral
Clarithromycin	Biaxin, Prevpac	Antibiotic	Bacterial infection	Risk of TdP And Avoid in congenital long QT	oral, inhaled
Cocaine	Cocaine	Local anesthetic	Anesthesia (topical)	Risk of TdP And Avoid in congenital long QT	oral, nasal
Disopyramide	Norpace	Antiarrhythmic	Arrhythmia	Risk of TdP And Avoid in congenital long QT	oral, injection
Dofetilide	Tikosyn	Antiarrhythmic	Arrhythmia	Risk of TdP And Avoid in congenital long QT	oral
Domperidone (Only on Non US Market)	Motilium, Motillium, Motinorm Costi, Nomit	Antiemetic	Nausea, vomiting	Risk of TdP And Avoid in congenital long QT	oral, injection, suppository
Donepezil	Aricept	Cholinesterase inhibitor	Dementia (Alzheimer's Disease)	Risk of TdP And Avoid in congenital long QT	oral
Dronedarone	Multaq	Antiarrhythmic	Arrhythmia	Risk of TdP And Avoid in congenital long QT	oral
Droperidol	Inapsine, Droleptan, Dridol, Xomolix	Antipsychotic/ Antiemetic	Anesthesia (adjunct), nausea	Risk of TdP And Avoid in congenital long QT	injection
Erythromycin	E.E.S., Robimycin, EMycin, Erymax, Ery-Tab, Eryc Ranbaxy, Erypar, Eryped, Erythrocin Stearate Filmtab, Erythrodot, E-Base, Erythroped, Ilosone, MY-E, Pediamycin, Abbotycin, Abbotycin-ES, Erycin, PCE Dispertab, Stiemycine, Acnasol, Tiloryth	Antibiotic	Bacterial infection, increase GI motility	Risk of TdP And Avoid in congenital long QT	oral, injection

Generic Name	Brand Names (Partial List)	Drug Class	Therapeutic Use	Risk Category	Route
Escitalopram	Cipralex, Lexapro, Nexit, Anxiset-E (India), Exodus (Brazil), Esto (Israel), Seroplex, Elicea, Lexamil, Lexam, Entact (Greece), Losita (Bangladesh), Reposil (Chile), Animaxen (Colombia), Esitalo (Australia), Lexamil (South Africa)	Antidepressant, SSRI	Depression (major), anxiety disorders	Risk of TdP And Avoid in congenital long QT	oral
Flecainide	Tambocor, Almarytm, Apocard, Ecrinal, Flécaïne	Antiarrhythmic	Arrhythmia	Risk of TdP And Avoid in congenital long QT	oral
Fluconazole	Diflucan, Trican	Antifungal	Fungal infection	Risk of TdP And Avoid in congenital long QT	oral, injection
Gatifloxacin (Removed from Market)	Tequin	Antibiotic	Bacterial infection	Risk of TdP And Avoid in congenital long QT	oral, injection
Grepafloxacin (Removed from Market)	Raxar	Antibiotic	Bacterial infection	Risk of TdP And Avoid in congenital long QT	oral
Halofantrine (Only on Non US Market)	Halfan	Antimalarial	Malaria	Risk of TdP And Avoid in congenital long QT	oral
Haloperidol	Haldol (US & UK), Aloperidin, Bioperidolo, Brotopon, Dozic, Duraperidol (Germany), Einalon S, Eukystol, Halosten, Keselan, Linton, Peluces, Serenace, Serenase, Sigaperidol	Antipsychotic	Schizophrenia, agitation	Risk of TdP And Avoid in congenital long QT	oral, injection
Ibogaine (Only on Non US Market)	None	Psychedelic	Narcotic addiction, unproven	Risk of TdP And Avoid in congenital long QT	oral
Ibutilide	Corvert	Antiarrhythmic	Arrhythmia	Risk of TdP And Avoid in congenital long QT	injection
Levofloxacin	Levaquin, Tavanic	Antibiotic	Bacterial infection	Risk of TdP And Avoid in congenital long QT	oral, injection
Levomepromazine (methotriptazine) (Only on Non US Market)	Nosinan, Nozinan, Levoprome	Antipsychotic	Schizophrenia	Risk of TdP And Avoid in congenital long QT	oral, injection

Generic Name	Brand Names (Partial List)	Drug Class	Therapeutic Use	Risk Category	Route
Levomethadyl acetate (Removed from Market)	Orlaam	Opiate	Narcotic dependence	Risk of TdP And Avoid in congenital long QT	oral
Levosulpiride (Only on Non US Market)	Lesuride, Levazeo, Enliva (with rabeprazole)	Antipsychotic	Schizophrenia	Risk of TdP And Avoid in congenital long QT	oral, injection
Mesoridazine (Removed from Market)	Serentil	Antipsychotic	Schizophrenia	Risk of TdP And Avoid in congenital long QT	oral
Methadone	Dolophine, Symoron, Amidone, Methadose, Physeptone, Heptadon	Opiate	Narcotic dependence, pain	Risk of TdP And Avoid in congenital long QT	oral, injection
Moxifloxacin	Avelox, Avalox, Avelon	Antibiotic	Bacterial infection	Risk of TdP And Avoid in congenital long QT	oral, injection
Ondansetron	Zofran, Anset, Ondemet, Zuplenz, Emetron, Ondavell, Emeset, Ondisolv, Setronax	Antiemetic	Nausea, vomiting	Risk of TdP And Avoid in congenital long QT	oral, injection, suppository
Oxaliplatin	Eloxatin	Anti-cancer	Cancer	Risk of TdP And Avoid in congenital long QT	injection
Papaverine HCl (Intra-coronary)	none	Vasodilator, Coronary	Diagnostic adjunct	Risk of TdP And Avoid in congenital long QT	injection
Pentamidine	Pentam	Antifungal	Fungal infection (Pneumocystis pneumonia)	Risk of TdP And Avoid in congenital long QT	injection, inhaled
Pimozide	Orap	Antipsychotic	Tourette's Disorder	Risk of TdP And Avoid in congenital long QT	oral
Probucol (Removed from Market)	Lorelco	Antilipemic	Hypercholesterolemia	Risk of TdP And Avoid in congenital long QT	oral
Procainamide	Pronestyl, Procan	Antiarrhythmic	Arrhythmia	Risk of TdP And Avoid in congenital long QT	injection
Propofol	Diprivan, Propoven	Anesthetic, general	Anesthesia	Risk of TdP And Avoid in congenital long QT	injection
Quinidine	Quinaglute, Duraquin, Quinact, Quinidex, Cin-Quin, Quinora	Antiarrhythmic	Arrhythmia	Risk of TdP And Avoid in congenital long QT	oral, injection
Roxithromycin (Only on Non US Market)	Rulide, Xthrocin, Roxl-150, Roxo, Surlid, Rulide, Biaxig, Roxar, Roximycin, Roxomycin, Rulid,	Antibiotic	Bacterial infection	Risk of TdP And Avoid in congenital long QT	oral

Generic Name	Brand Names (Partial List)	Drug Class	Therapeutic Use	Risk Category	Route
	Tirabcin, Coroxin				
Sevoflurane	Ultane, Sojourn	Anesthetic, general	Anesthesia	Risk of TdP And Avoid in congenital long QT	inhaled
Sotalol	Betapace, Sotalex, Sotacor	Antiarrhythmic	Arrhythmia	Risk of TdP And Avoid in congenital long QT	oral
Sparfloxacin (Removed from Market)	Zagam	Antibiotic	Bacterial infection	Risk of TdP And Avoid in congenital long QT	oral
Sulpiride (Only on Non US Market)	Dogmatil, Dolmatil, Eglonyl, Espiride, Modal, Sulpor	Antipsychotic, atypical	Schizophrenia	Risk of TdP And Avoid in congenital long QT	oral, inhaled
Sulopride (Only on Non US Market)	Barnetil, Barnotil, Topral	Antipsychotic, atypical	Schizophrenia	Risk of TdP And Avoid in congenital long QT	oral, injection
Terfenadine (Removed from Market)	Seldane	Antihistamine	Allergic rhinitis	Risk of TdP And Avoid in congenital long QT	oral
Terlipressin (Only on Non US Market)	Teripress, Glypressin, Terlipin, Remestyp, Tresil, Teriss and others	Vasoconstrictor	Septic shock	Risk of TdP And Avoid in congenital long QT	injection
Terodiline (Only on Non US Market)	Micturin, Mictrol (not bethanechol)	Muscle relaxant	Bladder spasm	Risk of TdP And Avoid in congenital long QT	oral
Thioridazine	Mellaril, Novoridazine, Thioril	Antipsychotic	Schizophrenia	Risk of TdP And Avoid in congenital long QT	oral
Vandetanib	Caprelsa	Anti-cancer-	Cancer (thyroid)	Risk of TdP And Avoid in congenital long QT	oral

Note: Medicines on this list are reviewed on an ongoing basis to assure that the available evidence supports their continued placement on this list. The list changes regularly and we recommend checking the website at [crediblemeds.org](http://crediblemeds.org) for the most up-to-date information. There may be many additional brand names that are not listed on this form.

**Disclaimer and Waiver:** The information presented is intended solely for the purpose of providing general information about health-related matters. It is not intended for any other purpose, including but not limited to medical advice and/or treatment, nor is it intended to substitute for the users' relationships with their own health care providers. To that extent, by use of this website and the information it contains, the user affirms the understanding of the purpose and releases AZCERT, Inc. from any claims arising out of his/her use of the website and its lists. The absence of drugs from these lists should not be considered an indication that they are free of risk of QT prolongation or torsades de pointes. Many medicines have not been tested for this risk in patients, especially those with congenital long QT syndrome.

